Objectives:	
The primary objective of this study is as follows:
 
• To evaluate the pharmacokinetics of Entospletinib (ENTO) and/or its metabolites (if applicable) in subjects with impaired hepatic function (stratified by smoking status, as appropriate) relative to matched, healthy controls 
The secondary objectives of this study are as follows:
 
• To evaluate the safety and tolerability of administration of ENTO in subjects with normal and impaired hepatic function• To evaluate the potential impact of smoking on the PK of ENTO in subjects with moderate hepatic impairment
--------------------	--

Study Design:	Phase 1, open-label, parallel-group, adaptive, multiple dose study
Number of Subjects Planned:	
A minimum of 40 subjects and a maximum of 80 subjects total.
 
Cohort 1 (Moderate Hepatic Impairment) initial cohort
 
Up to 40 subjects: 20 with moderate hepatic impairment (10 smokers [at least 8 evaluable] and 10 non-smokers [at least 8 evaluable]), 20 matched healthy controls (at least 8 evaluable healthy controls matched to smokers with moderate impairment, and at least 8 evaluable healthy controls matched to non-smokers with moderate hepatic impairment).
 
Adaptive Cohort 2 (Severe Hepatic Impairment)
 
Up to 20 subjects: 10 with severe impairment, up to 10 matched healthy controls, for 8 evaluable subjects per group. Data from healthy subjects in previous cohort who are an appropriate match for a severe hepatic impairment subject may be used.

Adaptive Cohort 3 (Mild Hepatic Impairment)

Up to 20 subjects: 10 with mild impairment, up to 10 matched healthy controls, for 8 evaluable subjects per group. Data from healthy subjects in previous cohort who are an appropriate match for a mild impairment subject may be used.

The 90% CIs will be examined to determine if a meaningful change (≥ 2 -fold mean difference from matched controls) in the exposures of ENTO and/or metabolite (if applicable) is identified which would be clinically interpreted. A decision to enroll subjects in adaptive Cohort 2 (Severe Hepatic Impairment) and/or adaptive Cohort 3 (Mild Hepatic Impairment) will be enrolled as determined by safety (treatment-emergent AEs, treatment-emergent laboratory abnormalities, vital signs, safety ECGs) and/or PK data from Cohort 1 (Moderate Hepatic Impairment). Specifically, Cohort 2 will be initiated if supported by safety (treatment-emergent AEs, treatment-emergent laboratory abnormalities, vital signs, safety ECGs) and PK findings from subjects in Cohort 1. Cohort 3 will be enrolled if a clinically meaningful change (≥ 2 -fold mean difference from matched healthy controls) in the exposures of ENTO and/or metabolite (if applicable) exposure is identified in non-smoking hepatic impairment subjects in Cohort 1.

Target Population: Male and non-pregnant, non-lactating females subjects aged ≥ 18 years, with varying degrees of hepatic impairment and matched healthy controls. Those with hepatic impairment will be categorized based upon the Child-Pugh-Turcotte (CPT) classification system for hepatic impairment (CPT Class A, B, or C) as recommended by the United States Food and Drug Administration (FDA) and international guidance documents. Within the CPT system, subjects will be assigned to Class A, B, or C based on a cumulative score evaluating the presence and severity of hyperbilirubinemia, hypoalbuminemia, prolongation of international normalized ratio (INR) for coagulation time, ascites, and hepatic encephalopathy. Designations of hepatic impairment will be assigned as follows:

- Class A (mild): CPT score 5-6
- Class B (moderate): CPT score 7-9
- Class C (severe): CPT score 10-15

The control group will consist of matched healthy subjects with normal hepatic function.

Cohort 1 enrollment of hepatic impairment subjects will be an approximate even distribution of subjects who are active cigarette smokers (at least 10 cigarettes/day) and subjects who are current

non-smokers (no use of tobacco, nicotine-containing or THC-containing products within the last 14 days). Hepatic impairment subjects enrolled in adaptive Cohorts 2 and 3 will be current non-smokers (no use of tobacco, nicotine-containing or THC-containing products within the last 14 days).

Duration of Dosing: 5 days

Study Duration: 20 days

Main Eligibility Criteria: Eligible subjects will be male and non-pregnant, non-lactating female subjects, aged ≥ 18 years, $18 \leq \text{BMI} \leq 40$, with either impaired hepatic function of CPT classification A, B, or C or with normal hepatic function. Hepatic impairment must have been stable during the 3 months (90 days) prior to study drug administration. Each subject in the control group will be matched to a subject with impaired hepatic function by age (± 10 years), gender, and body mass index ($\pm 20\%$).

Subjects with use of moderate or strong CYP3A or CYP2C9 inducers, or strong CYP2C9 inhibitors within 2 weeks prior to study drug administration will be excluded since these agents may affect the PK of ENTO. Subjects with use of proton pump inhibitors within 1 week prior to study drug administration will be excluded.

Study Procedures/
Frequency:

Following completion of Screening and Day -1 assessments, eligible subjects will be enrolled in Cohort 1 (followed by Cohorts 2 and/or 3 pending PK/Safety review) and receive multiple doses of 100 mg twice a day (BID) ENTO (1 \times 100 mg tablet) starting on Day 1. When feasible, dosing in a matched control subject with normal hepatic function will occur after the subject with impaired hepatic function has completed the PK assessments, except if data exist from a subject with normal hepatic function in a previous cohort, this will be used instead of enrolling an additional normal healthy control subject as permitted in adaptive Cohorts 2 and 3.

Subjects in adaptive Cohort 2 (Severe Hepatic Impairment) and/or adaptive Cohort 3 (Mild Hepatic Impairment) will be enrolled as determined by safety and/or PK data from Cohort 1 (Moderate Hepatic Impairment). Specifically, Cohort 2 will be initiated if supported by safety and PK findings from the non-smoking hepatic impairment subjects and matching, healthy control subjects in Cohort 1. Cohort 3 will be enrolled if a clinically meaningful change (≥ 2 -fold mean difference from matched healthy controls) in the exposures of ENTO and/or metabolite (if applicable) exposure is identified in non-smoking hepatic impairment subjects in Cohort 1. (Refer to Section 8.7, Sample Size)

Study Visits and Confinement

Eligible subjects will be confined to the study center beginning Day -1 until the completion of assessments on Day 9. Subjects will return for an in-clinic follow-up visit 14 (\pm 1) days after the last dose of study drug (i.e., Day 19).

Study Drug Administration

All study treatments will be administered at approximately the same time each day with 240 mL of water following an overnight fast (no food or drinks except water, for at least 8 hours).

When ENTO is administered twice a day, the evening dose of ENTO will be administered approximately 12 hours after the AM dose. Subjects should continue fasting for 2 hours post AM dose and 2 hours before and 2 hours after the PM dose.

Only the AM dose of ENTO will be given on Day 5.

On the days of intensive pharmacokinetic sampling, study treatments will be administered in the morning following an overnight fast (no food or drinks except water, for at least 8 hours). Subjects will continue to fast until after collection of the 4-hour pharmacokinetic samples, relative to study drug dosing.

Additionally, subjects will be restricted from water consumption 1 hour before until 2 hours after dosing, except for the 240 mL given with the study treatment.

Pharmacokinetic Assessments

Serial blood samples will be collected relative to the AM dose on the following days and timepoints for ENTO and/or metabolites (if applicable).

Day 1: 0 (predose), 0.5, 1, 1.5, 2, 3, 4, 6, 8, and 12 (pre-PM dose) hours postdose

Day 5: 0 (predose), 0.5, 1, 1.5, 2, 3, 4, 6, 8, 12, 18, 24, 36, 48, 60, 72, 84, and 96 hours postdose

Trough Sampling: Days 2 and 4: 0 (pre-AM dose, at approximately the same time each day)

Plasma concentrations for ENTO and/or its metabolites (if applicable) will be determined and PK parameters evaluated. Protein binding of ENTO and/or its metabolites (if applicable), may be assessed at their T_{max} time point(s) as well as another later time point.

An additional Trough PK sample will be collected at the follow-up visit for assessing plasma concentrations for ENTO and/or its metabolites (if applicable).

Safety Assessments

Complete physical exam: Screening and at the follow-up visit or the Early Termination visit (if applicable)

Symptom driven physical exam: Day -1, Day 3, Day 7, and prior to discharge on Day 9

Vital signs (blood pressure, pulse, respiration rate, and temperature): Screening, Day -1, Day 3, Day 7, prior to discharge on Day 9, at the follow-up visit, and at the early termination visit, if applicable.

Clinical laboratory tests (hematology, blood chemistry, and urinalysis): Screening, Day -1, Day 7, prior to discharge on Day 9, at the follow-up visit, and at the early termination visit, if applicable.

Urine Drug and Alcohol Assessments: Screening, Day -1, Day 5, prior to discharge on Day 9, at the follow-up visit, and at the early termination visit, if applicable.

12-lead ECG: Screening, Day -1, Day 3, Day 7, prior to discharge on Day 9, at the follow-up visit, and at the early termination visit, if applicable.

Serum Pregnancy Test (women of childbearing potential only): Screening, Day -1, Day 4, prior to discharge on Day 9, at the follow-up visit, and at the early termination visit, if applicable.

Serology Test (HBV, HCV, HIV): Screening

FSH testing (all females, except those who are permanently sterile or have medically documented ovarian failure): Screening

Other Assessments

Height: Screening

Weight: Screening, Day -1

Assessment of adverse events and concomitant medications will continue throughout the study.

Genetic Testing

A separate, mandatory blood specimen will be collected for the extraction of deoxyribonucleic acid (DNA) for genotyping to identify polymorphisms of drug metabolizing enzymes (such as CYP2C9, CYP3A4/5, CYP1A2 and UGT1A1) and transporters (such as OATP 1B1/3, P-gp, BCRP and MATE1) to optimize the therapeutic strategy for ENTO. This sample should be collected on Day -1, before administration of the first dose of study drug, but may be collected at any time during clinic confinement.

Test Product, Dose, and Mode of Administration:	ENTO 100 mg [1 × 100 mg tablet] twice a day
--	---

Reference Therapy, Dose, and Mode of Administration:	Not applicable
---	----------------

Criteria for Evaluation:	
Safety:	Safety will be evaluated by assessment of periodic physical examinations including vital sign and 12-lead ECGs performed at various time points during the study, by the documentation of adverse events, and by intervention with concomitant medications.
Efficacy:	Not applicable
Pharmacokinetics:	The following plasma pharmacokinetic parameters will be calculated: C_{max} , T_{max} , C_{last} , T_{last} , λ_z , AUC_{last} , AUC_{inf} , $\%AUC_{exp}$, $T_{1/2}$, CL/F , and V_z/F , and as appropriate, AUC_{tau} , C_{tau} .

Statistical Methods:	
Pharmacokinetic parameters for ENTO and/or its metabolites (if applicable) will be listed and summarized by hepatic function group (normal or CPT Class A, B, or C) and smoking status (Cohort 1 only) using descriptive statistics (e.g., sample size, arithmetic mean, geometric mean, % coefficient of variation, standard deviation, median, minimum, an maximum). An analysis of variance appropriate for a parallel design will be fit to the natural logarithm-transformed pharmacokinetic parameters (AUC and C_{max}). The 90% confidence intervals (CIs) will be constructed for the least-squares geometric mean (GLSM) ratios of pharmacokinetic parameters for ENTO and/or its metabolite (if applicable), in groups of subjects with hepatic impairment (for Cohort 1 only, stratified by smoking status) versus the appropriate group of matched, healthy controls.
 
Protein binding of ENTO and/or its metabolites (if applicable) at their T_{max} and another later time point will be summarized by hepatic function group and smoking status (Cohort 1 only) using descriptive statistics (if applicable).
 
Safety data will be listed by subject and summarized by hepatic function groups, and frequency of event/abnormality or descriptive statistical summaries, as appropriate.
 
A sample size of 8 evaluable subjects per hepatic function group (for Cohort 1, it is 8 evaluable subjects per hepatic function group within

-----------------------------	---

each smoking status group) will provide a $\geq 89\%$ probability for the 90% CI for the GLSM ratio of pharmacokinetic parameters (AUC or C_{\max}) for ENTO in the hepatic impairment/dysfunction group(s) versus the appropriate group of matched, healthy controls, to be within limits of 50% to 200%. The calculation assumes an expected ratio of geometric means of 1.0 in pharmacokinetic parameters and inter-subject standard deviation of 0.455 for the natural logarithm-transformed pharmacokinetic parameters for ENTO. The assumption is based on the data obtained from a prior clinical study of ENTO (Study GS-US-339-0111).

This study will be conducted in accordance with the guidelines of Good Clinical Practices (GCPs) including archiving of essential documents.

GLOSSARY OF ABBREVIATIONS AND DEFINITION OF TERMS

° C	degrees Celsius
° F	degrees Fahrenheit
AE	adverse event
ALL	acute lymphoid leukemia
AML	acute myeloid leukemia
ALT	alanine aminotransferase
ANOVA	analysis of variance
aPTT	activated partial thromboplastin time
AST	aspartate aminotransferase
AUC	area under the ENTO concentration versus time curve
AUC _{0-last}	area under the plasma concentration-time curve from time 0 to the last measurable concentration
AUC _{inf}	area under the plasma/serum/PBMC concentration versus time curve extrapolated to infinite time, calculated as $AUC_{0-last} + (C_{last}/\lambda_z)$
AUC _{tau}	area under the plasma/serum/PBMC concentration versus time curve over the dosing interval
BID	twice a day
BLQ	below limit of quantification
BMI	body mass index
BUN	blood urea nitrogen
CBC	complete blood count
CFR	Code of Federal Regulations
CI	confidence interval
CK	creatine kinase
CLL	chronic lymphocytic leukemia
CL/F	apparent oral clearance
C _{last}	last observed quantifiable serum/plasma/PBMC concentration of the drug
C _{max}	maximum observed ENTO concentration of drug
CPK	creatine phosphokinase
CPT	Child-Pugh-Turcotte
CrCl	creatinine clearance
CRF	case report form(s)
CRO	contract (or clinical) research organization
CSR	clinical study report
CTA	clinical trial application
C _{tau}	observed drug concentration at the end of the dosing interval
CV	coefficient of variation
DNA	deoxyribonucleic acid
DSPH	Drug Safety and Public Health

EC	ethics committee
ECG	electrocardiogram
eCRF	electronic case report form(s)
EDC	electronic data capture
ENTO	entospetenib
eSAE	electronic serious adverse event
ET	early termination
EU	European Union
FDA	(United States) Food and Drug Administration
FSH	follicle stimulating hormone
FU	follow up
GCP	Good Clinical Practice (Guidelines)
Gilead	Gilead Sciences, Inc.
GLSM	geometric least square mean
HBV	hepatitis B virus
HCV	hepatitis C virus
HDPE	high density polyethylene
HIV	human immunodeficiency virus
HLGT	high-level group term
HLT	high-level term
IB	investigator's brochure
ICF	Informed Consent Form
ICH	International Conference on Harmonisation
ID	Identification
IND	Investigational New Drug (Application)
INR	international normalized ratio
IRB	institutional review board
IUD	intrauterine device
LLT	lower-level term
LLOQ	lower-limit of quantitation
LOEL	lowest observable effect level
MedDRA	Medical Dictionary for Regulatory Activities
NDA	New Drug Application
NHL	non-Hodgkin lymphoma
NOEL	no observable effect level
OTC	over the counter
PD	pharmacodynamics
PI	principal investigator
PI3K	phosphatidylinositol 3-kinase
PK	pharmacokinetic(s)

PT	preferred term
PT	prothrombin time
Q1	first quartile
Q3	third quartile
QT	electrocardiographic interval between the beginning of the Q wave and termination of the T wave representing the time for both ventricular depolarization and repolarization to occur
QTcF	QT interval corrected for heart rate using the Fridericia formulation
RA	rheumatoid arthritis
SADR	serious adverse drug reaction
SAE	serious adverse event
SAP	Statistical Analysis Plan
SD	standard deviation
SOC	System Organ Class
SOP	standard operating procedure
SUSAR	Suspected Unexpected Serious Adverse Reaction
SYK	spleen tyrosine kinase
TEAE	treatment-emergent adverse event
THC	Tetrahydrocannabinol
T _{last}	time (observed time point) of C _{last}
T _{max}	the time (observed time point) of C _{max}
T _{1/2}	an estimate of the terminal elimination half-life of the drug in ENTO calculated by dividing the natural log of 2 by the terminal elimination rate constant (λ_z)
US	United States
V _z /F	apparent volume of distribution of the drug
λ_z	terminal elimination rate constant; estimated by linear regression of the terminal elimination phase of the log serum/plasma/PBMC concentration versus time curve of the drug

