Up to 20 subjects:
10 with severe impairment, up to 10 matched healthy controls if none of the healthy subjects from a previous cohort is an appropriate match for a severe impairment subject, for 8 evaluable per group.

- Adaptive Cohort 3 (CPT Class A, Mild Hepatic Impairment)

[figure not shown]
Up to 20 subjects:

10 subjects with mild impairment, up to 10 matched healthy control subjects if none of the healthy subjects from a previous cohort is an appropriate match for a mild impairment subject, for 8 evaluable per group

The 90% CIs will be examined to determine if a meaningful change (≥ 2 -fold mean difference from matched controls) in the exposures of ENTO and/or metabolite (if applicable) is identified which would be clinically interpreted. A decision to enroll subjects in adaptive Cohort 2 (Severe Hepatic Impairment) and/or adaptive Cohort 3 (Mild Hepatic Impairment) will be enrolled as determined by safety (treatment-emergent AEs, treatment-emergent laboratory abnormalities, vital signs, safety ECGs) and/or PK data from non-smoking moderate hepatic impairment subjects and matching, healthy controls in Cohort 1. Specifically, Cohort 2 will be initiated if supported by safety (treatment-emergent AEs, treatment-emergent laboratory abnormalities, vital signs, safety ECGs) and PK findings from non-smoking subjects and healthy, matched controls in Cohort 1. Cohort 3 will be enrolled if a clinically meaningful change (≥ 2 -fold mean difference from matched healthy controls) in the exposures of ENTO and/or metabolite (if applicable) exposure is identified in non-smoking hepatic impairment subjects in Cohort 1..

[figure not shown]
An overview of the study design is shown below in [Figure 3-1](#)

Figure 3-1. High Level Study Schema

The study schema for all subjects is shown in [Figure 3-2](#)

Figure 3-2. Study Schema – All Cohorts

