4.3.3. Healthy Matched Controlled Subjects

Healthy matched controlled subjects meeting *any* of the following additional exclusion criteria are not to be enrolled in this study:

- 1) Serious or active medical or psychiatric illness that, in the opinion of the Investigator, would interfere with subject treatment, assessment, or compliance with the protocol. This would include renal, cardiac, hematological, hepatic, pulmonary (including chronic asthma), endocrine (eg, diabetes), central nervous, gastrointestinal (including an ulcer), vascular, metabolic (thyroid disorders, adrenal disease), immunodeficiency disorders, active infection, or malignancy that are clinically significant or requiring treatment.
- 2) History of liver disease.

- 3) Have taken any prescription medications or over-the-counter medications, including herbal products, within 28 days prior to start of study drug dosing, with the exception of vitamins and/or acetaminophen and/or ibuprofen
- 4) Positive test for drugs of abuse, including alcohol at Screening or on Day -1/check-in
- 5) Subjects will be required to refrain from the use of nicotine, nicotine-containing products (including cigarette smoking) or THC-containing products for at least 14 days prior to first dose of study drug, and during the course of the study through the follow-up visit

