8.7. Sample Size

A sample size of 8 evaluable subjects per hepatic function group (for Cohort 1, it is 8 evaluable subjects per hepatic function group within each smoking status group) will provide

a \geq 89% probability for the 90% CI for the GLSM ratio of pharmacokinetic parameters (AUC or C_{\max}) for ENTO in the hepatic impairment/dysfunction group(s) versus the appropriate group of matched controls, to be within limits of 50% to 200%. The calculation assumes an expected ratio of geometric means of 1.0 in pharmacokinetic parameters and inter-subject standard deviation of 0.455 for the natural logarithm-transformed pharmacokinetic parameters for ENTO. The assumption is based on the data obtained from a prior clinical study of ENTO (Study GS-US-339-0111).

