### **Adaptive Cohort 3 (Mild Hepatic Impairment)**

Up to 20 subjects: 10 with mild impairment, up to 10 matched healthy controls, for 8 evaluable subjects per group. Data from healthy subjects in Cohort 1 or 2 who are an appropriate match for a mild impairment subject may be used.

[figure not shown]
Cohort 1 enrollment of hepatic impairment subjects will be an approximate even distribution of subjects who are active cigarette smokers (at least 10 cigarettes/day) and subjects who are current non-smokers (no use of tobacco, nicotine-containing or tetrahydrocannabinol (THC)-containing products within the last 14 days). Hepatic impairment subjects enrolled in adaptive Cohorts 2 and 3 will be current non-smokers (no use of tobacco, nicotine-containing or THC-containing products within the last 14 days).

Designations of hepatic impairment will be assigned as follows:

- Class A (mild): CPT score 5 to 6
- Class B (moderate): CPT score 7-9
- Class C (severe): CPT score 10-15

[figure not shown]
An overview of the study design is shown below in [Figure 1-1](#).

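### Cohort 3 may reuse, with no order of preference, the same controls whose low exposure helped to open it, which would bias the mild-impairment ratio upward

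*Protocol*

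**What the plan says.** **Trigger.** Protocol synopsis, 1.3, 3.1 and 5.3 say that Cohort 3 will be enrolled if a mean difference of at least 2-fold from matched healthy controls in ENTO and/or metabolite "exposure is identified in non-smoking hepatic impairment subjects in Cohort 1". Protocol 1.3 adds that finding no effect in moderate impairment would remove the need to study mild disease.

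**Reuse of controls.** The synopsis allows it: "Data from healthy subjects in previous cohort who are an appropriate match for a mild impairment subject may be used". SAP 1.3 widens the pool: "Data from healthy subjects in Cohort 1 or 2 who are an appropriate match for a mild impairment subject may be used". Two further statements make reuse the default. The synopsis (Study Procedures) and Protocol 3.1 say that existing control data will take the place of enrolling a new control. The cohort list in 3.1 provides new Cohort 3 controls only where no earlier control matches. The planned size is "up to 10 matched healthy controls, for 8 evaluable subjects per group".

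**Who the controls are.** Under Protocol 4.3.3 every healthy control must abstain from smoking: "Subjects will be required to refrain from the use of nicotine, nicotine-containing products (including cigarette smoking) or THC-containing products". The exemption in 5.6.2 covers only smoking subjects with hepatic impairment. Cohort 1 controls matched to smokers are therefore non-smokers too.

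**Analysis.** SAP 5.2.2 fits hepatic function group alone. It rules out a 2-fold increase if the upper 90% limit is below 2.0. It plans no sensitivity analysis for reused controls.

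**The concern.** The Cohort 1 non-smoker control mean is the denominator of the ratio that opens Cohort 3. It may then be the denominator of the Cohort 3 ratio as well. An observed ratio reaches 2 more easily when the controls happen to be low, so, given that the trigger fired, their mean is expected to lie below its true value. A fresh control group would not carry that error, but a reused one does.

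What is at stake is the mild-impairment ratio and the SAP's upper-limit rule. An inflated ratio makes it harder to conclude that mild impairment raises exposure less than 2-fold. Protocol 1.3 says that the study's data are to inform dosing recommendations. The plan also gives no rule for choosing among eligible earlier controls, and in an open-label study that choice is made after the Cohort 1 PK data have been seen.

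**Working it through.** **Inputs from the documents**
- "A sample size of 8 evaluable subjects per hepatic function group" (Protocol 8.7; SAP 1.4), so n = 8 per group.
- "standard deviation of 0.455 for the natural logarithm-transformed pharmacokinetic parameters for ENTO" (same sections), so σ = 0.455.
- Trigger at a 2-fold difference, ln 2 = 0.693. Two-sided 90% CI; decision limit 2.0 (SAP 5.2.2).

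**Assumptions, not in the documents**
- True moderate ratio R from 1.5 to 3.0, and true mild ratio 1.3.
- 0, 4 or 8 of the 8 Cohort 3 controls reused from the trigger comparison.
- Trigger is a point estimate of at least 2, as an increase, in the same parameter as the Cohort 3 ratio.

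**Step 1: the plan's own figure.** SE = 0.455 × √(2/8) = 0.2275, with 14 df. "The calculation assumes an expected ratio of geometric means of 1.0 in pharmacokinetic parameters". Under that assumption the probability that the upper 90% limit is below 2.0 is 89.4% (noncentral t), which agrees with the stated ≥89%. The event as worded, with both limits inside 50% to 200%, gives 78.9%. That is a separate matter, but the SE used below is the plan's.

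**Step 2: bias of the trigger controls.** Let D be the Cohort 1 log difference, moderate mean minus control mean. The control mean has variance σ²/n = 0.455²/8 = 0.02588. With z = (ln 2 − ln R)/0.2275 and λ(z) = φ(z)/[1 − Φ(z)]:

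- P(trigger) = 1 − Φ(z)
- expected shortfall of the control log-mean, given the trigger: b = (0.02588/0.2275) × λ(z) = 0.1138 × λ(z)
- inflation of the mild ratio: exp(b) if all 8 are reused, exp(b/2) if 4 are reused

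For R = 2.0: z = 0, λ = 0.798, b = 0.0908, exp(b) = 1.095.

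| True moderate ratio | P(trigger) | λ(z) | Inflation, 8 reused | Inflation, 4 reused |
|---|---|---|---|---|
| 1.5 | 10% | 1.741 | 22% | 10% |
| 1.7 | 24% | 1.302 | 16% | 8% |
| 2.0 | 50% | 0.798 | 9.5% | 5% |
| 2.5 | 84% | 0.295 | 3% | 2% |
| 3.0 | 96% | 0.085 | 1% | 0.5% |

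With no trigger control reused, the inflation is nil.

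**Step 3: effect on the SAP's decision rule.** Simulation given the trigger, true mild ratio 1.3, pooled-variance t interval. Probability that the upper 90% limit is below 2.0:

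| True moderate ratio | 8 reused | 4 reused | Independent controls |
|---|---|---|---|
| 1.7 | 31% | 44% | 56% |
| 2.0 | 41% | 49% | 56% |
| 2.5 | 51% | 53% | 56% |

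Group-specific variances, as in the SAP code, lower each figure by about half to one percentage point and leave the contrasts unchanged.

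**Step 4: interval behaviour.** With a true mild ratio of 1.0 and full reuse, 90% CI coverage is about 90% at R = 2.0 and 82% at R = 1.5. Intervals lying wholly above the truth rise from 5% to 8.3% and 18% respectively.

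**The case against.** The strongest case against acting is that this is a reasonable economy in a small Phase 1 study, with a bias that is usually minor. Several parts of it stand.

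- **Full reuse is a worst case.** Reuse needs an age, sex and BMI match, and the pool also holds Cohort 1 controls matched to smokers and any Cohort 2 controls. Mixing these in dilutes the bias.
- **The largest biases occur where Cohort 3 seldom opens.** At a true ratio of 1.5 the trigger fires about 10% of the time. At 2.5 or more, where it usually fires, inflation is 3% or less.
- **The trigger is loosely specified.** It covers parent drug and/or metabolite, speaks of a change rather than an increase, and is set beside an examination of the 90% CIs and of safety and/or PK data. A metabolite-driven trigger need not bias the parent ratio equally, and a 2-fold decrease would reverse the direction.
- **The direction is cautious.** For an increase, the error overstates exposure in mild impairment, and no rule in the documents turns the mild ratio into a dosing restriction.

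A reader might also infer that 3.1 requires the trigger controls to be reused. It does not: it favours any matching control from a previous cohort. Nor does the plan overlook the smoker-matched controls, which are already in the pool; what is missing is an order of preference.

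These points limit the size. They do not remove the bias when the true moderate effect is near 2-fold, and nothing in the plan prevents full reuse.

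**Conclusion.** The point holds as a moderate, inexpensive improvement. Reuse of earlier controls is the default, and the controls that opened Cohort 3 are neither excluded nor ranked last. Given the trigger, reusing all of them inflates the mild ratio by 9.5% to 22% for true moderate ratios of 2.0 down to 1.5, and by 3% or less from 2.5 upward; reusing half gives about half of that. At a true moderate ratio of 1.7 and a mild ratio of 1.3, the chance of ruling out a 2-fold increase is about 31% with full reuse, 44% with half and 56% with independent controls.

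These figures rest on the plan's SD and group size, on assumed true ratios, and on a trigger read as an observed increase of at least 2-fold in the same parameter.

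A reader might extend the argument to Cohort 2 and infer a downward bias in the severe-impairment ratio. The documents do not support this. They give no PK threshold for opening Cohort 2, only that safety and PK findings must support it, so neither the direction nor the size of any selection can be derived.

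**What to change.** In the protocol synopsis, Protocol 3.1 and SAP 1.3, state an order of preference for Cohort 3 controls, all meeting the same age, sex and BMI criteria:

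1. Earlier controls outside the non-smoker trigger: Cohort 1 controls matched to smokers, and any controls newly enrolled for Cohort 2.
2. New controls, within the up to 10 already planned for Cohort 3.
3. Cohort 1 controls that entered the non-smoker trigger, only if no other match is available.

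The wording in 3.1 that allows new controls only when no earlier control matches needs to change accordingly. In SAP 5.2.2, report the Cohort 3 ratio with and without any reused trigger controls.

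The cost is a few sentences, one extra table, and possibly a few more healthy volunteers dosed. The maximum of 80 subjects is unchanged. The matching tolerances also stay as they are, although a control outside the trigger may be taken ahead of a closer match within them. If trigger controls are still used as a last resort, some bias can remain, and the table shows how far the result depends on them.
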